5.3 Lifestyle Considerations

No other restrictions than the ones listed in the exclusion criteria or in the contraindications for subsequent vaccinations are required.

5.4 Screen Failures

Screen failures are defined as participants who consent to participate in the clinical study but are not subsequently enrolled. Screening information is recorded in the source documents.

Individuals who do not meet the criteria for participation in this study (screen failure) can be rescreened when the condition excluding them from participation is resolved (eg, fever, antibiotics received within 72 hours, etc).

6 Study Intervention

Study intervention is defined as any investigational intervention(s), marketed product(s), placebo, or medical device(s) intended to be administered to a study participant according to the study protocol.

Note: routine vaccines administered outside of study protocol are not considered as study interventions.

6.1 Study Intervention Administered

Study interventions are described in [Table 6.1](#).

Table 6.1: Identity of study intervention

Intervention Name	MenACYW conjugate vaccine (MenQuadfi®): Meningococcal Polysaccharide (Serogroups A, C, W, and Y) Tetanus Toxoid Conjugate Vaccine (Sanofi Pasteur Inc., Swiftwater, PA, USA)
Use	Investigational
IMP and NIMP	IMP
Type	Vaccine
Dose Formulation	Liquid solution
Unit Dose Strengths	Each dose of MenACYW conjugate vaccine contains the following components: Meningococcal capsular polysaccharides: 
 • Serogroup A¹: 10 µg • Serogroup C¹: 10 µg • Serogroup W¹: 10 µg • Serogroup Y¹: 10 µg ¹ Conjugated to Tetanus toxoid protein carrier: 55 µg ² ² Tetanus toxoid protein quantity is approximate and dependent on the polysaccharide-to-protein ratio for the conjugates used in each formulation
Excipients/Diluent	Sodium acetate buffered saline solution
Dosage Level	0.5 mL per dose
Number of Doses/Dosing Interval	1 dose
Route of Administration	IM injection
Site of Administration	Deltoid muscle in the upper arm for children 3-17 years of age
Sourcing	Provided by the Sponsor

Packaging and Labeling	MenACYW conjugate vaccine (single-dose vial) will be supplied as an individual commercial box without repackaging. There will be no overlabel for primary packaging and a multilingual booklet label with clear tape on the outer box will be added. See the Operating Guidelines for additional label detail.
Current/Former Name or Alias	Brand name: MenQuadfi®
Batch Number	TBD

IMP: Investigational Medicinal Product; NIMP: Non-Investigational Medicinal Product; TBD: to be determined

6.2 Preparation/Handling/Storage/Accountability

MenACYW conjugate vaccine is supplied in single-dose (0.5 mL) vials.

It will be administered intramuscularly in the deltoid muscle of arm.

The site of injection should be prepared with a suitable antiseptic. After administration of the vaccine, the used syringe and needles will be disposed of in accordance with currently established guidelines.

Prior to administration, all study products must be inspected visually for cracks, broken seals, correct label content, and extraneous particulate matter and/or discoloration, whenever solution and container permit. If any of these conditions exist, the vaccine must not be administered. A replacement dose is to be used, and the event is to be reported to the Sponsor. The rubber stopper should not be removed from any of the vaccine vials.

Detailed guidance and information are provided in the Operating Guidelines.

- 1) The Investigator or designee must confirm appropriate temperature conditions have been maintained during transit for all study intervention received and any discrepancies are reported and resolved before use of the study intervention.
- 2) Only participants enrolled in the study may receive study intervention and only authorized site staff may supply or administer study intervention. All study intervention must be stored in a secure, environmentally controlled, and monitored (manual or automated) area in accordance with the labeled storage conditions with access limited to the investigator and authorized site staff.
- 3) The Investigator, institution, or the head of the medical institution (where applicable) is responsible for study intervention accountability, reconciliation, and record maintenance (ie, receipt, reconciliation, and final disposition records).
- 4) Further guidance and information for the final disposition of unused study interventions are provided in the Operating Guidelines.

6.3 Measures to Minimize Bias: Randomization and Blinding

6.3.1 Randomization and Allocation Procedures

At V1, participants will be randomly selected with a balanced distribution between Groups 1 and 2 using SAS[®] software, Version 9.4 or above (SAS Institute, Cary, North Carolina, USA) to receive the same vaccine (MenACYW conjugate vaccine) at different timepoints.

Participant numbers will consist of a 12-digit string (a 3-digit country identifier, a 4-digit study center identifier, and a 5-digit participant identifier). The 5-digit participant identifier will correspond to the chronological order of enrollment in the center. For example, Subject 246000100005 is the fifth subject enrolled in Center Number 1 in Finland (246 being the country code for Finland).

Participant numbers should not be reassigned for any reason.

The Biostatistics platform of the Sponsor will generate a list of participants randomly selected (1 per site).

6.3.2 Blinding and Code-breaking Procedures

This is an open-label study.

6.4 Study Intervention Compliance

The following measures will ensure that the study intervention is administered as planned (see [Table 6.1](#)), and that any noncompliance is documented so that it can be accounted for in the data analyses:

- All vaccinations will be administered by qualified and trained study personnel.
- The person in charge of study intervention management at the site will maintain accountability records of study intervention delivery to the study site, study intervention inventory at the site, dose(s) given to each participant, and unused or wasted doses.

6.5 Concomitant Therapy

At the time of enrollment, ongoing medications and other therapies (eg, blood products) should be recorded in the source document as well as new medications prescribed for new medical conditions/AEs during study participation.

Documentation in the CRB of ongoing concomitant medication(s) will be limited to specific categories of medication(s) of interest beginning on the day of vaccination. This may include medications of interest that were started prior to the day of vaccination.

Reportable medications (Category 1, 2, and 3) will be collected in the source document from the day of first vaccination to the end of the study and in the CRB as per the instructions given below for each category.

Reportable medications include medications that impact or may impact the consistency of the safety information collected after vaccination and/or the immune response to vaccination. Three standard categories of reportable medications are defined:

- Category 1: medications impacting or that may have an impact on the evaluation of the safety (eg, antipyretics, analgesics, and non-steroidal anti-inflammatory drugs [NSAIDs], systemic steroids/corticosteroids [therapy duration less than 2 weeks] and other immune-modulators). Category 1 medications do not define the Per-Protocol Analysis Set (PPAS).

Note: Topical steroids (inhaled, optic, ophthalmic, nasal, etc.) should not be captured or reported.

Category 1 medications will be reported in the CRB from the day of each vaccination to the end of the solicited and unsolicited follow-up period after each vaccination.

- Category 2: medications impacting or that may have an impact on the immune response and used to define the PPAS; for example:
 - Flu vaccines administered within 14 days pre or post each trial vaccination, including the day of the study vaccination visit and up to the last blood draw.
 - Any vaccine other than study vaccines (vaccines non-described in the Protocol) within the 28 days (4 weeks) preceding or after the trial vaccination, including the day of the study vaccination visit and up to the last blood draw.
 - Immune globulins, blood or blood-derived products: used in the 3 months preceding each blood draw between BL1 to BL2 and BL3 to BL4 (Group 1) or between BL2 to BL3 (Group 2).
 - Immunosuppressive therapy such as immune-suppressors, immune-modulators with immunosuppressive properties, long-term systemic corticosteroids therapy (prednisone or equivalent for more than 2 consecutive weeks) used in the 3 months preceding the study vaccination, anti-cancer chemotherapy, anti-proliferative drugs such as deoxyribonucleic acid (DNA) synthesis inhibitors, or radiation therapy: used in the 6 months preceding the study vaccination between BL1 to BL2 and BL3 to BL4 (Group 1) and between BL2 to BL3 (Group 2).

Category 2 medications will be reported in the CRB according to the collection period detailed above.

- Category 3: systemic (oral or injectable) antibiotics, received within 72 hours preceding each visit for blood draw related to IMP assessment (meningococcal vaccines) and used to define the PPAS, as they may interfere with bioassays used for antibody testing when taken before a blood draw.

Category 3 medications will be reported in the CRF for the period of 3 days (72 hours) before each blood draw.

Note: Topical antibiotics (inhaled, optic, ophthalmic, nasal, etc.) should not be captured or reported.

The information reported in the CRB for each reported medication will be limited to:

- Trade name
- Rationale for the origin of prescription: Whether it was a prophylactic^a medication? Prophylactic medications will be recorded in the Action Taken section of the AE collection tables
- Medication category (1, 2, or 3)
- Start and stop dates

Dosage and administration route, homeopathic medication, topical and inhaled steroids, as well as topical, ophthalmic, and ear treatments will not be recorded. Topical analgesics should not be applied at the site of vaccination; however, if they are applied inadvertently to the vaccination site, they should be recorded as a Category 1 medication in this specific instance.

If the participant has received medications other than those listed in Categories 1, 2, and 3, the detailed information will be collected in the source documents only.

Medications given in response to an AE will be captured in the “Action Taken” section of the AE CRB only. No details will be recorded in the concomitant medication CRB unless the medication(s) received belongs to one of the pre-listed categories. Medications will not be coded.

6.5.1 Rescue Medicine

Appropriate medical equipment and emergency medications, including epinephrine (1:1000), must be available on site in the event of an anaphylactic, vasovagal, or other immediate allergic reaction.

6.6 Dose Modification

Not applicable.

6.7 Intervention After the End of the Study

Not applicable.

^a Medication prescribed for preventing AE occurrence (eg, paracetamol to reduce the risk of fever)

7 Discontinuation of Study Intervention and Participant Discontinuation/Withdrawal

7.1 Discontinuation of Study Intervention

7.1.1 Temporary Contraindications for Vaccination

Should a participant experience one of the conditions listed below, the Investigator will postpone further vaccination until the condition is resolved. Postponement must still be within the timeframe for vaccination indicated in the SoA.

- TCI01: Febrile illness (temperature $\geq 38.0^{\circ}\text{C}$ [$\geq 100.4^{\circ}\text{F}$]) or moderate or severe acute illness / infection on the day of vaccination, according to Investigator judgment
- TCI02: Receipt of any vaccine in the 4 weeks preceding the trial vaccination or planned receipt of any vaccine in the 4 weeks following trial vaccination except for influenza vaccination, which may be received at least 2 weeks before or after study vaccines. This exception includes monovalent pandemic influenza vaccines and multivalent influenza vaccines
- TCI03: Receipt of oral or injectable antibiotic therapy within 72 hours prior to the blood draw
- TCI04: Receipt of immune globulins, blood or blood-derived products in the past 3 months

7.1.2 Temporary Contraindications for Blood Sample

Should a participant receive oral or injectable antibiotic therapy within 3 days (72 hours) prior to a blood draw, the Investigator will postpone that blood draw until it has been 3 days since the participant last received oral or injectable antibiotic therapy. Postponement must still be within the timeframe for blood draw. If postponement would result in the sample collection falling outside of the appropriate timeframe, the blood sample should be collected without postponement, and it should be documented appropriately that the sample was taken less than 3 days after stopping antibiotic treatment.

7.1.3 Definitive Contraindication

Participants will permanently discontinue (definitive discontinuation) study intervention for the reasons listed below. These participants must not receive any additional dose of study intervention but should continue to be followed for safety and immunogenicity. Additional unscheduled visits may be performed for safety reasons and information will be reported in the source documents.

Should a participant experience at least one of the conditions listed below, the Investigator will discontinue vaccination:

- DCI01: Pregnancy, as indicated by a positive urine test
- DCI02: An anaphylactic or other significant allergic reaction to the previous dose of vaccine

- DCI03: SAE assessed as related to the study vaccine following the previous dose of vaccine, based on Investigator's judgment.
- DCI04: Bleeding disorder, or receipt of anticoagulants in the 3 weeks preceding vaccination.
- DCI05: Receipt of immune globulins, blood or blood-derived products in the 3 months preceding vaccination
- DCI06: Previous vaccination against meningococcal disease with either the trial vaccine or another vaccine (ie, mono- or polyvalent, polysaccharide, or conjugate meningococcal vaccine containing serogroups A, C, W, or Y) with the exception of licensed MenC vaccination received during infancy (MET51 Group 3), of the single dose of meningococcal vaccine administered as part of study MET51 (Groups 1 and 3) and of Meningococcal B vaccine
- DCI07: Known or suspected congenital or acquired immunodeficiency; or receipt of immunosuppressive therapy, such as anti-cancer chemotherapy or radiation therapy, within the preceding 6 months; or long-term systemic corticosteroid therapy (prednisone or equivalent for more than 2 consecutive weeks within the 3 months preceding vaccination)
- DCI08: New history of meningococcal infection, confirmed either clinically, serologically, or microbiologically
- DCI09: At high risk for meningococcal infection during the trial (specifically but not limited to participants with persistent complement deficiency, with anatomic or functional asplenia, or participants traveling to countries with high endemic or epidemic disease)
- DCI10: New personal history of GBS
- DCI11: New personal history of an Arthus-like reaction after vaccination with a tetanus toxoid-containing vaccine
- DCI12: Known systemic hypersensitivity to any of the vaccine components, or history of a life-threatening reaction to the vaccines used in the trial or to a vaccine containing any of the same substances^a
- DCI13: Verbal report by parent or LAR of thrombocytopenia or suspected thrombocytopenia, contraindicating IM vaccination
- DCI14: Chronic illness^b that, in the opinion of the Investigator, is at a stage where it might interfere with trial conduct or completion

In the event of a local or national immunization program with any other vaccine as needed, participants who receive such a vaccine at any time during the study will not be withdrawn from the study.

^a The components of the MenACYW conjugate vaccine are listed in [Section 6.1](#) and in the IB.

^b Chronic illness may include, but is not limited to, cardiac disorders, renal disorders, auto-immune disorders, diabetes, psychomotor diseases, and known congenital or genetic diseases.

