1.1 Synopsis

Protocol Title:

A Phase IIIb, Open-label, Multi-center Study to Evaluate the Immunogenicity and Safety of a Booster Dose and Describe the Immune Persistence of MenACYW Conjugate Vaccine with 5- and/or 10-year Booster Doses in Children and Adolescents who had been Primed with MenACYW Conjugate Vaccine as Toddlers

Short Title:

Study on an Investigational Quadrivalent Meningococcal Conjugate Vaccine (MenACYW Conjugate Vaccine) Administered as a 5- and/or 10-year Booster Dose in Children and Adolescents Vaccinated 5 or 10 Years Earlier as Toddlers

Rationale:

The purpose of Amendment 1.0 is to add a study arm in order to describe the immunogenicity and safety of a booster dose and the persistence of a priming dose of MenACYW conjugate vaccine (MenQuadfi®) in adolescents who had been vaccinated with MenACYW conjugate vaccine approximately 10 years earlier as toddlers as part of the MET51 study. It is also to increase the study duration in the initial study arm to describe the immunogenicity and safety of a second booster dose (as adolescents approximately 5 years after the first booster dose) and the persistence of a first booster dose of MenACYW conjugate vaccine in adolescents who had been primed with MenACYW conjugate vaccine as toddlers as part of the MET51 study and had received a first booster dose as children approximately 5 years after the priming dose.

Objectives and Endpoints:

Objectives	Endpoints

Primary
 
 To demonstrate the vaccine seroresponse sufficiency of meningococcal serogroups A, C, W, and Y after the administration of a booster dose of MenACYW conjugate vaccine in children who received 1 dose of MenACYW conjugate vaccine approximately 5 years earlier as toddlers (Group 1) 	
 Vaccine seroresponse¹ against meningococcal serogroups A, C, W, and Y measured by serum bactericidal assay using human complement (hSBA) assessed at Visit (V)1 (baseline) and at V2 (30 days after the administration of a booster dose of MenACYW conjugate vaccine) (Group 1) 
¹ Seroresponse is defined as the proportions of participants with an hSBA pre-vaccination titer < 1:8 who achieved a post-vaccination titer ≥ 1:16 or participants with a pre-vaccination titer ≥ 1:8 who

	achieved a post-vaccination titer at least 4-fold greater than the pre-vaccination titer
Key Secondary	

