5.2 Exclusion Criteria

Participants are not eligible for the study if any of the following criteria are met:

- E01: Participation at the time of study enrollment (or in the 4 weeks preceding the trial vaccination) or planned participation during the present trial period in another clinical trial investigating a vaccine, drug, medical device, or medical procedure
- E02: Previous vaccination against meningococcal disease with either the trial vaccine or another vaccine (ie, mono- or polyvalent, polysaccharide, or conjugate meningococcal

- vaccine containing serogroups A, C, W, or Y) with the exception of licensed MenC vaccination received during infancy (MET51 Group 3), of the single dose of meningococcal vaccine administered as part of study MET51 (Groups 1 and 3) and of Meningococcal B vaccine
- E03: Receipt of any vaccine in the 4 weeks preceding the trial vaccination or planned receipt of any vaccine in the 4 weeks following trial vaccination except for influenza vaccination, which may be received at least 2 weeks before or after study vaccines. This exception includes monovalent pandemic influenza vaccines and multivalent influenza vaccines
- E04: Receipt of immune globulins, blood or blood-derived products in the past 3 months
- E05: Known or suspected congenital or acquired immunodeficiency; or receipt of immunosuppressive therapy, such as anti-cancer chemotherapy or radiation therapy, within the preceding 6 months; or long-term systemic corticosteroid therapy (prednisone or equivalent for more than 2 consecutive weeks within the past 3 months)
- E06: History of meningococcal infection, confirmed either clinically, serologically, or microbiologically
- E07: At high risk for meningococcal infection during the trial (specifically but not limited to participants with persistent complement deficiency, with anatomic or functional asplenia, or participants traveling to countries with high endemic or epidemic disease)
- E08: Personal history of GBS
- E09: Personal history of an Arthus-like reaction after vaccination with a tetanus toxoid-containing vaccine
- E10: Known systemic hypersensitivity to any of the vaccine components, or history of a life-threatening reaction to the vaccines used in the trial or to a vaccine containing any of the same substances^a
- E11: Verbal report by parent or LAR of thrombocytopenia or suspected thrombocytopenia, contraindicating IM vaccination

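### DCI06 repeats exclusion criterion E02 without exempting the V1 booster, so as written it bars the Year 5 second booster that the protocol schedules for Group 1

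*Protocol*

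**What the plan says.** Section 7.1.3 of the protocol, on definitive contraindications, includes "DCI06: Previous vaccination against meningococcal disease with either the trial vaccine or another vaccine". Three exceptions follow: licensed MenC vaccine given in infancy, and then "of the single dose of meningococcal vaccine administered as part of study MET51 (Groups 1 and 3) and of Meningococcal B vaccine". One listed condition is enough to trigger the rule, and the consequence is stated without discretion: "These participants must not receive any additional dose of study intervention but should continue to be followed for safety and immunogenicity".

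The same protocol plans two doses of the trial vaccine in Group 1, at V1 and at Year 5 (V3). This is in the Synopsis, section 4.1 with Table 4.1, section 4.3 and the Group 1 schedule (Table 1.1). The Synopsis gives the second booster as a purpose of Amendment 1.0: "It is also to increase the study duration in the initial study arm to describe the immunogenicity and safety of a second booster dose". Table 1.1 also marks a review of contraindications to vaccination at V3. The second safety, full and per-protocol analysis sets (SafAS 2, FAS2 and PPAS2; protocol 9.3 and SAP 1.3) are built on the V3 dose in Group 1 and the V2 dose in Group 2.

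**The concern.** For Group 1 at V3, two binding rules point in opposite directions. Section 7.1.3 forbids a further dose to anyone who has had the trial vaccine outside the three exceptions. Section 8 makes adherence to the schedule of activities mandatory, and that schedule includes the dose. Section 8 also disallows waivers and exemptions, so a site cannot resolve the conflict locally. An investigator at V3 must either set aside a listed definitive contraindication in a minor or omit a scheduled vaccination.

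At stake are the Group 1 data from V3 to V4, which are the study's only information on a second booster. All of these analyses are descriptive.

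**Working it through.** No power or sample-size figure is involved. The check compares texts and then applies the rule to each dosing visit.

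**1. DCI06 against E02.** The source criterion in section 5.2 opens "E02: Previous vaccination against meningococcal disease with either the trial vaccine or another vaccine". Apart from the label and a line break, its full text and all three exceptions are identical to DCI06.

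**2. The rule applied at each planned dose.**

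| Dose | Earlier trial-vaccine doses | Covered by an exception? | Result |
|---|---|---|---|
| Group 1, V1 (E02 applies) | MET51 dose | Yes | Dose allowed |
| Group 2, V2 (DCI06 applies) | MET51 dose | Yes | Dose allowed |
| Group 1, V3 (DCI06 applies) | MET51 dose and V1 booster | MET51 dose yes, V1 booster no | Dose forbidden |

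The failure is confined to Group 1 at V3.

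**3. Could the V1 booster be outside the meaning of previous vaccination?** No. DCI06 names the trial vaccine and then exempts the MET51 study dose. If doses given within a study did not count, that exception would be unnecessary. The closing sentence of 7.1.3 on immunization programmes does not help either: it concerns other vaccines and withdrawal from the study, not further dosing with the trial vaccine. The SAP adds no exception.

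**4. Oversight or intent?** Of the 14 definitive contraindications, 3 are new (DCI01 to DCI03), so 14 − 3 = 11 come from section 5.2.

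- Reworded for a later dose (6): E12/DCI04, E04/DCI05, E05/DCI07, E06/DCI08, E08/DCI10, E09/DCI11.
- Unchanged (11 − 6 = 5): E02/DCI06, E07/DCI09, E10/DCI12, E11/DCI13, E14/DCI14.

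An example of adaptation is "E06: History of meningococcal infection, confirmed either clinically, serologically, or microbiologically", which became "DCI08: New history of meningococcal infection, confirmed either clinically, serologically, or microbiologically". Of the five left unchanged, DCI06 is the only one that the study's own V1 dose triggers by itself. Section 7.1.3 also expects dosing after an earlier dose, as in "DCI02: An anaphylactic or other significant allergic reaction to the previous dose of vaccine". This points to an oversight.

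**5. How many meet the wording.** At most about 250, the maximum estimate for Group 1 in section 9.2. The documents give no Year 5 attendance figure, so no smaller number can be derived. This counts participants who satisfy the text of DCI06, not participants expected to go undosed.

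**6. What would be lost if doses were withheld** (protocol Table 3.1):

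- Response to A, C, W and Y after the second booster: the whole objective.
- Tetanus response: 1 of 3 settings (Group 1 first booster, Group 2 booster, Group 1 second booster).
- Serogroup C response by priming status: 2 of 6 sub-items.
- Safety: 1 of 3 bullets.
- Secondary immunogenicity endpoints using the Group 1 V3 and V4 pair: 3 of 12 (A, C, W and Y titers; tetanus; serogroup C).

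Not affected: the primary objective and its power (Group 1, V1 to V2), 5-year persistence, the Group 1 pre-dose sample at V3, and Group 2.

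**The case against.** The best counter-argument is that nobody could misread the intent. The second booster appears in the Synopsis, sections 4.1 and 4.3, Table 1.1 and the analysis sets. DCI02 and DCI03 would be redundant for Group 1 if the V1 dose alone barred the next one. Sites will therefore probably vaccinate, the tallies in step 6 describe an unlikely event, and what remains is a wording slip that changes no estimate. The Operating Guidelines, which are not among these documents, may also clarify the V3 checklist.

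Much of this stands. The practical risk is low, the tallies are conditional, and this is a drafting error rather than a dispute about the design. But clear intent elsewhere does not remove a mandatory stop rule, and an operating document would not amend the protocol.

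The effect on PPAS2 needs a caveat. No listed exclusion names a definitive contraindication, and the Category 2 vaccine item in section 6.5 covers vaccines other than the study vaccine, so giving the V3 dose is not expressly a reason for exclusion. A strict reading of the item on vaccine administration that departs from the protocol could nevertheless reach such doses. That uncertainty is a further reason to correct the text.

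**Conclusion.** The point holds and should be fixed. Read literally, DCI06 prohibits a dose that the protocol requires, for every Group 1 participant vaccinated at V1, at most about 250. The likely consequence is a formal conflict with section 7.1.3 at each V3 dose. Loss of second-booster data follows only where a site applies the text and withholds the dose. Confidence in the textual conclusion is high, since it rests only on the wording of sections 5.2 and 7.1.3 and on the Group 1 schedule. The view that sites will mostly give the dose is a judgement about conduct, which the documents cannot settle.

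**What to change.** Amend DCI06 before the first Year 5 visit by adding one exception: *and of the MenACYW booster dose administered at V1 of MEQ00073 (Group 1)*. Leave the rest unchanged, so that the criterion still catches a meningococcal A, C, W or Y vaccine received outside the study during the five-year interval. E02 needs no change.

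The cost is one added exception in a protocol amendment, with no extra data, visits or participants.
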